8.1.1 Adverse (Drug) Reaction

All noxious and unintended responses to a medicinal product related to any dose should be considered adverse drug reactions. “Responses” to a medicinal product means that a causal relationship between a medicinal product and an AE is at least a reasonable possibility, ie, the relationship cannot be ruled out.

8.1.2 Unexpected Adverse Drug Reaction

An unexpected adverse drug reaction is defined as an adverse reaction, the nature or severity of which is not consistent with the applicable product information.

8.1.3 Assessment of AEs by the Investigator

The Investigator will assess the severity (intensity) of each AE as mild, moderate, or severe, and will also categorize each AE as to its potential relationship to study drug using the categories of yes or no.

Assessment of severity

Mild – An event that is easily tolerated and generally not interfering with normal daily activities.

Moderate – An event that is sufficiently discomforting to interfere with normal daily activities.

Severe – An event that is incapacitating with inability to work or perform normal daily activities.

Causality assessment

The relationship of an AE to the administration of the study drug is to be assessed according to the following definitions:

No (not related or unlikely to be related) – The time course between the administration of study drug and the occurrence or worsening of the AE rules out a causal relationship and another cause (concomitant drugs, therapies, complications, etc) is suspected.

Yes (possibly, probably, or definitely related) – The time course between the administration of study drug and the occurrence or worsening of the AE is consistent with a causal relationship and no other cause (concomitant drugs, therapies, complications, etc) can be identified.

The definition implies a reasonable possibility of a causal relationship between the event and the study drug. This means that there are facts (evidence) or arguments to suggest a causal relationship.

The following factors should also be considered:

- The temporal sequence from study drug administration-

The event should occur after the study drug is given. The length of time from study drug exposure to event should be evaluated in the clinical context of the event.

- Underlying, concomitant, intercurrent diseases-

Each report should be evaluated in the context of the natural history and course of the disease being treated and any other disease the participant may have.

- Concomitant drug-
The other drugs the participant is taking or the treatment the participant receives should be examined to determine whether any of them might be recognized to cause the event in question.
- Known response pattern for this class of study drug-
Clinical and/or preclinical data may indicate whether a particular response is likely to be a class effect.
- Exposure to physical and/or mental stresses-
The exposure to stress might induce adverse changes in the recipient and provide a logical and better explanation for the event.
- The pharmacology and PK of the study drug-
The known pharmacologic properties (absorption, distribution, metabolism, and excretion) of the study drug should be considered.

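### Protocol 8.1.3 allows only Yes or No for causality, but its definitions cover two of four combinations of timing and other cause and do not match the 8.1.1 standard

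*Protocol*

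**What the plan says.** Protocol 8.1.3 has the investigator record the relationship of each AE to study drug "using the categories of yes or no". It then gives a label and a definition for each category.

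- The label "No (not related or unlikely to be related") is defined by timing that "rules out a causal relationship and another cause (concomitant drugs, therapies, complications, etc) is suspected".
- The label "Yes (possibly, probably, or definitely related") is defined by timing that "is consistent with a causal relationship and no other cause (concomitant drugs, therapies, complications, etc) can be identified".

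One sentence after the definitions reads "The definition implies a reasonable possibility of a causal relationship between the event and the study drug". A list of factors to consider follows, covering timing, other diseases, concomitant drugs, class effects, stress and pharmacology.

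Protocol 8.1.1 defines an adverse drug reaction by a different test, namely that causality "is at least a reasonable possibility, ie, the relationship cannot be ruled out".

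The SAP offers no relatedness definition of its own. SAP 3.5.1 tabulates study-drug-related TEAEs and TESAEs. Protocol 9.2.2.1 and SAP 3.5.2 summarize new-onset diabetes and macular degeneration by relationship to study drug.

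**The concern.** With only two categories, the definitions have to be exhaustive and mutually exclusive. Each one here joins a timing condition and an other-cause condition with *and*, and the two pairs are not complements of each other. An event that satisfies one half of each definition belongs nowhere, yet the form still demands an answer.

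The uncovered case is foreseeable. Protocol 8.1.4.1 and 8.1.4.2 themselves list competing explanations to look for when liver enzymes or CK rise, including viral hepatitis, alcohol, concomitant drugs and unaccustomed exercise. At least 70% of participants must be on high-intensity statins (Protocol 3.1), so for muscle and liver events a background drug may be a credible alternative.

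At stake is the consistency of the relatedness variable. If one site resolves the mixed case as Yes and another as No, the related-event tables partly reflect how sites read the text. Protocol 8.3 also makes reporting of an SAE after the 35-day window depend on the investigator considering it related.

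**Working it through.** No figure in the plan enters this point, so there is nothing to recompute. The check enumerates the combinations and compares the two sections.

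**Step 1: the conditions.** Timing either rules out a causal relationship or is consistent with one. Another cause is either present or absent. That makes 2 × 2 = 4 combinations.

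**Step 2: apply the 8.1.3 definitions literally.**

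| Timing | Other cause | Meets No? | Meets Yes? | Category |
|---|---|---|---|---|
| Ruled out | Present | yes | no (timing fails) | No |
| Consistent | Absent | no (timing and cause fail) | yes | Yes |
| Consistent | Present | no (timing fails) | no (cause fails) | none |
| Ruled out | Absent | no (cause fails) | no (timing fails) | none |

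Two of the four combinations have a category and two do not.

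**Step 3: two simplifications in the table.**

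- The No definition speaks of a cause that is suspected and the Yes definition of one that can be identified. If a merely suspected cause does not count as identified, some events in the third row move to Yes. Those with an identified competing cause still have no category.
- Timing is treated as two-valued. Timing that is doubtful but not excluded fails the No definition, and it meets Yes only if it is read as consistent.

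**Step 4: compare each label with its definition.**

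- The Yes label includes possibly related events. Where another explanation exists, a causal role for the drug may still be possible, but the definition excludes the event once another cause can be identified.
- The No label includes events unlikely to be related. The definition requires timing that rules the drug out, which is stricter than unlikely.

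**Step 5: compare with 8.1.1.** Take an event with consistent timing and a competing cause. Timing has not ruled the drug out, so the event can meet the 8.1.1 test that causality "a causal relationship between a medicinal product and an AE is at least a reasonable possibility, ie, the relationship cannot be ruled out". The same event fails the literal Yes in 8.1.3. The literal No wording, with its requirement that timing exclude the drug, does agree with 8.1.1. The conflict therefore lies in the other-cause clause of Yes and in the unlikely label of No.

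**Step 6: look for a tie-breaker.** The sentence after the definitions repeats the reasonable-possibility idea but does not remove the other-cause clause. The factor list tells the investigator to look for other diseases and drugs, but not how a competing cause decides between Yes and No. Neither states a default.

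**The case against.** The strongest reply is that investigators will not read the definitions as a truth table. The Yes label includes possibly related events, the next sentence invokes reasonable possibility, and the listed factors are to be weighed, which would be largely pointless if any alternative cause settled the answer. On that reading a mixed-cause event goes to Yes and 8.1.3 agrees with 8.1.1. This is fair as a prediction of what many sites will do. It does not make the text consistent, because the protocol directs that relationship be assessed according to the definitions and the other-cause clause stays in force.

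A reader might infer more than the documents support, in three ways.

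- *Related events will be under-counted.* This does not follow. The mixed-cause event fails Yes, but it fails No just as literally. Only inconsistency is supported, and its direction is not.
- *Background statins make another cause available for nearly every AE.* The statin requirements count participants, not events. Protocol 8.1.3 asks whether another drug might be recognized as causing the particular event, which is plausible for some muscle and liver events but not for AEs in general. Protocol 5.6.2 also expects lipid therapy to have been stable for at least 8 weeks before Screening, which weakens a timing argument against it. The share of AEs with a competing cause is not documented.
- *The SUSAR decision turns on the site's Yes or No.* No section says so. Under Protocol 8.5 the sponsor or its designee reports SUSARs, which are suspected adverse reactions, and 8.1.1 defines a reaction by the broader test.

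The safeguards are real. Protocol 8.3 requires SAEs up to 35 (±7) days after the last dose to be reported whatever the investigator's view of relatedness. The DSMB reviews unblinded safety data and aggregate imbalances (8.5.1, 9.2.4) and follows events of special interest whether or not they were reported as AEs (8.1.4). SAP 3.5.1 also tabulates TEAEs and TESAEs irrespective of relatedness, and no inference is made on safety endpoints (SAP 3.5).

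**Conclusion.** The point stands as an internal inconsistency in a stated rule. Two of the four combinations of timing and other cause have no category, both labels disagree with their definitions, and the Yes condition is narrower than the reaction standard in 8.1.1. This rests on reading the definitions as written, with a candidate cause counting as identifiable.

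The consequence is possible inconsistency between sites in the relatedness call. It reaches the study-drug-related TEAE and TESAE tables, the new-onset diabetes and macular degeneration summaries by relationship, and SAE reporting after the 35-day window. The number of affected events and the direction of any miscount cannot be derived from the documents. Comparisons that ignore relatedness are untouched. The defect merits correction because the remedy is short, but it does not threaten the overall safety evaluation.

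**What to change.** Reword the causality paragraph of Protocol 8.1.3 so that the two categories are exhaustive and use the 8.1.1 test.

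- **Yes:** a causal relationship with study drug is a reasonable possibility in the sense of 8.1.1, even if another cause is also possible.
- **No:** all other events.

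Keep the factor list as guidance for applying that test. Bring the parenthetical labels into line with it, so that possibly related sits under Yes without a no-other-cause condition and unlikely is either dropped or tied to the 8.1.1 test.

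The cost is a protocol clarification and a notice to sites. No visit, sample or efficacy analysis changes. More events may be called related. If AEs have already been assessed under the present wording, they must be re-assessed or flagged, so that one table does not mix two causality standards.

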8.1.4 Events of Special Interest

ESIs will be monitored over time by the independent DSMB, as described in the DSMB charter, regardless of whether these events were reported as AEs. Any events that qualify as an AE or SAE will be reported accordingly (see [Sections 8.1, 8.2, and 8.3](#)).

ESIs will include the following hepatic abnormalities, muscle-related abnormalities, new-onset diabetes mellitus (NODM) and/or hyperglycemia, renal abnormalities, changes to antihypertensive medication(s) due to changes in blood pressure, and ophthalmic events (ie, macular degeneration), described as follows:

- AST or ALT $>3 \times$ ULN;
- Bilirubin $>2 \times$ ULN;
- CK $>5 \times$ ULN;
- NODM or worsening of glycemic control;

Note: NODM is defined by 1 or more of the following criteria, based upon information from AE, medication, and laboratory data:

- AE indicating new type 1 or type 2 diabetes;
- Initiation of anti-diabetes medication with confirmation of the diagnosis of diabetes by blinded external review by experts in diabetology;
- HbA1c $\geq 6.5\%$ (≥ 0.065 hemoglobin fraction); and/or
- Two consecutive values of fasting plasma glucose that are ≥ 126 mg/dL (≥ 7.0 mmol/L).

Note: Worsening of glycemic control will be defined as an HbA1c increase from Baseline $>0.5\%$ (>0.005 hemoglobin fraction) and/or a new concomitant medication or increase in current antidiabetic therapy in a participant with a Baseline HbA1c $\geq 6.5\%$ (≥ 0.065 hemoglobin fraction).

- A >25% decrease in eGFR from Baseline or an eGFR <30 mL/min/1.73 m², calculated using the Chronic Kidney Disease Epidemiology Collaboration equation, and/or an increase in serum creatinine of ≥ 0.3 mg/dL (≥ 26.5 μ mol/L) from Baseline;
- Changes to antihypertensive medication(s) due to changes in blood pressure in those participants receiving antihypertensive medication(s) treatment at Baseline; and
- Macular degeneration.

These ESIs will be monitored through review of the AE and laboratory database.

8.1.4.1 Guidelines for management of elevated liver enzymes

Participants with signs or symptoms consistent with liver injury (eg, nausea, vomiting, anorexia, fatigue, right upper abdominal pain or discomfort) should undergo immediate testing of ALT, AST, gamma-glutamyl transferase, bilirubin, alkaline phosphatase, prothrombin time, and international normalized ratio.

In the absence of clinical symptoms, participants with ALT or AST $>3 \times$ ULN (if normal at Baseline) or >2 -fold change (if abnormal at Baseline) should be retested within 48 to 72 hours for the usual serum measurements (ALT, AST, alkaline phosphatase, and bilirubin) to confirm the abnormalities and to determine if the associated values are increasing or decreasing. There should also be an inquiry about symptoms at the time of follow-up.

If the above abnormalities are confirmed:

- Repeat liver enzyme and serum bilirubin tests 2 or 3 times weekly. The frequency of retesting can decrease to once a week or less if abnormalities stabilize or the study drug has been discontinued and the participant is asymptomatic;
- Obtain a more detailed history of symptoms and prior or concurrent diseases;
- Obtain a history of concomitant drug use (including nonprescription medications and herbal and dietary supplement preparations), alcohol use, recreational drug use, and special diet;
- Rule out acute viral hepatitis types A, B, C, D, and E; autoimmune or alcoholic hepatitis; nonalcoholic steatohepatitis; hypoxic/ischemic hepatopathy; and biliary tract disease;
- Obtain a history of exposure to environmental chemical agents;
- Obtain additional tests to evaluate liver function, as appropriate (eg, international normalized ratio, direct bilirubin); and
- Consider gastroenterology or hepatology consultations.

Study drug discontinuation should occur if:

- ALT or AST $>8 \times$ ULN;
- ALT or AST $>5 \times$ ULN for more than 2 weeks;
- ALT or AST $>3 \times$ ULN and (total bilirubin $>2 \times$ ULN or international normalized ratio >1.5); or
- ALT or AST $>3 \times$ ULN with the appearance of fatigue, nausea, vomiting, right upper quadrant pain or tenderness, fever, rash, and/or eosinophilia ($>5\%$).

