4.2 Exclusion Criteria

Participants who meet any of the following criteria will be excluded from participation in the study:

1. Have current or any previous history of New York Heart Association class III or IV heart failure (HF) or left ventricular ejection fraction <30%;
2. Have been hospitalized for HF within 5 years prior to Screening;
3. Have had any of the following clinical events within 3 months prior to Screening:
 - Non-fatal MI;
 - Non-fatal stroke;
 - Non-elective coronary revascularization; and/or
 - Hospitalization for unstable angina and/or chest pain.
4. Have uncontrolled severe hypertension, defined as either systolic blood pressure ≥ 160 mmHg or diastolic blood pressure ≥ 100 mmHg prior to Randomization taken as the average of triplicate measurements. One triplicate retest will be allowed during the same visit, at which point if the retest result is no longer exclusionary, the participant may be randomized;
5. Have a formal diagnosis of homozygous FH;
6. Have active liver disease, defined as any known current infectious, neoplastic, or metabolic pathology of the liver; unexplained elevations in alanine aminotransferase (ALT) or aspartate aminotransferase (AST) $>3 \times$ upper limit of normal (ULN); or total bilirubin $>2 \times$ ULN at Screening;

Note: An abnormal ALT, AST, or total bilirubin must be confirmed by a repeat abnormal measurement at least 1 week apart.

7. Have glycosylated hemoglobin (HbA1c) $\geq 10.0\%$ (≥ 0.100 hemoglobin fraction) or a fasting glucose ≥ 270 mg/dL (≥ 15.0 mmol/L) at Screening;
8. Have thyroid-stimulating hormone $>1.5 \times$ ULN at Screening;
9. Have creatine kinase (CK) $>3 \times$ ULN at Screening;
10. Have a history of a malignancy that required surgery (excluding local and wide local excision), radiation therapy, and/or systemic therapy during the 3 years prior to Randomization;
11. Have a known history of alcohol and/or drug abuse within 5 years prior to Randomization;
12. Have received treatment with other investigational products or devices within 30 days of Screening or 5 half-lives of the previous investigational product, whichever is longer;

Note: Participants who have received treatment for COVID-19 with standard of care and/or emergency use authorization medications, including vaccinations and boosters, within 30 days of Screening or 5 half-lives of the previous investigational product **will** be permitted.

13. Are taking gemfibrozil;

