8.7.4 Managing Abnormal and Critical Laboratory Values

Any laboratory test result abnormality that fulfills the criteria for an SAE will be reported as such on the appropriate AE and SAE eCRF. Any treatment-emergent abnormal laboratory result that is clinically significant, ie, meets 1 or more of the following criteria, will be recorded as a single diagnosis on the AE eCRF:

- Is accompanied by clinical symptoms;
- Leads to a change in study drug (eg, study drug interruption or permanent discontinuation); and/or
- Requires a change in concomitant therapy or a medical intervention (eg, the addition of, interruption of, or discontinuation of, or any other change in a concomitant medication, therapy, or treatment).

These criteria apply to any protocol and non-protocol-specified safety and/or efficacy laboratory results from tests performed after the first dose of study drug that meet clinical significance criteria. These criteria do not apply to any abnormal laboratory test results which fall outside the laboratory reference range, but which do not meet clinical significance criteria (these will be analyzed and reported as laboratory abnormalities) or those which are a result of an AE or an endpoint which has already been reported.

The Investigator is responsible for reviewing laboratory test results and determining whether an abnormal value in an individual participant represents a clinically significant change from the participant's Baseline values. In general, laboratory abnormalities without clinical significance should not be recorded as AEs. Where applicable, the clinical sequelae, not the laboratory abnormality, should be recorded as the AE.

Critical laboratory values are values that may warrant medical intervention to avoid possible harm to a participant. Critical laboratory values will be defined in the Laboratory Manual for the study, and the Medical Monitor and Investigator will be notified of the occurrence of a critical laboratory value (critical high or critical low) by a special annotation (flag) in the laboratory reports provided to the sites.

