4 DATA SAFETY MONITORING BOARD

An independent Data Safety Monitoring Board (DSMB) will monitor unblinded safety data, including blood pressure changes over time and the occurrence of ESIs during the study on a bi-annual basis (ie, approximately every 6 months). Participants, investigators, site staff and in general all personnel directly involved in the conduct of the study will remain blinded to the participants' treatment assignment until the completion of the study.

Details related to the DSMB responsibilities, authorities, and procedures will be documented in a DSMB Charter.

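### For symptom-free participants with Baseline ALT or AST above 2.5×ULN, a value above 5×ULN but not above twice Baseline prompts no retest under the liver guideline, although a stopping rule already applies at that level

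*Protocol*

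**What the plan says.** **Retest trigger.** Protocol Section 8.1.4.1 covers participants without clinical symptoms. With a normal Baseline, ALT or AST above 3×ULN is retested. With an abnormal Baseline, the condition is a more than 2-fold "change (if abnormal at Baseline) should be retested within 48 to 72 hours for the usual serum measurements". Confirmed abnormalities lead to testing 2 or 3 times weekly, which may later be relaxed.

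**Stopping rules.** The same section lists four reasons to discontinue: above 8×ULN; above 5× "ULN for more than 2 weeks"; above 3×ULN with raised bilirubin or INR; and above 3×ULN with listed symptoms or signs. None depends on Baseline.

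**Who can enter.** Section 4.2, criterion 6, excludes known active liver disease and "unexplained elevations in alanine aminotransferase (ALT) or aspartate aminotransferase (AST") above 3×ULN at Screening, confirmed by a repeat at least 1 week apart. Section 9.2 defines Baseline as the last non-missing value before study drug, and Appendix A draws a full chemistry panel on Day 1.

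**Scheduled tests.** Appendices A and B place ALT and AST at Screening, Days 1, 30, 84, 180, 270 and 365, and the End of Study Visit.

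**Other oversight.** Section 8.1.4 makes ALT or AST above 3×ULN an event of special interest and says: "These ESIs will be monitored through review of the AE and laboratory database". Section 8.7.4 says: "Critical laboratory values will be defined in the Laboratory Manual for the study, and the Medical Monitor and Investigator will be notified". It also makes the Investigator responsible for "determining whether an abnormal value in an individual participant represents a clinically significant change".

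**The concern.** The retest trigger and the stop use different scales. The trigger moves with the participant's Baseline; the stop is a fixed multiple of ULN. A stop defined by duration works only if a second value arrives in time, and the retest followed by serial testing is what the section provides for that. Where the trigger lies above the stop level, a participant can be above 5×ULN without the liver guideline asking for the value that would show whether the elevation has lasted 2 weeks.

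Neighbouring rules do not have this feature. For a normal Baseline, the retest level (3×ULN) is below the duration stop (5×ULN). The CK guideline (Section 8.1.4.2) repeats above 5×ULN and withdraws on a confirmed unexplained value above 10×ULN. The renal guideline (Section 8.1.4.4) asks for a repeat at the same levels that lead to discontinuation.

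At stake is patient safety: a symptom-free participant could remain on drug past the protocol's own 2-week limit if nobody repeats the test. No efficacy estimate depends on this.

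**Working it through.** The plan gives no figure to reproduce, so the check compares thresholds and visit dates.

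**Inputs**
- Retest trigger for abnormal Baseline: more than 2-fold change, read as above 2 × Baseline (Section 8.1.4.1; the reading is an assumption).
- Duration stop: above 5×ULN for more than 14 days. Immediate stop: above 8×ULN (Section 8.1.4.1).
- Entry limit: 3×ULN at Screening (Section 4.2).
- Visits after Day 30: Days 84, 180, 270 and 365. Windows: ±3 days at Day 30, ±7 days at the others (Appendix A).

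**Step 1: where the trigger passes the stop.** 2 × Baseline > 5 gives Baseline > 2.5×ULN.

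**Step 2: the uncovered band.** It runs from 5×ULN to 2 × Baseline, so its width is 2 × Baseline − 5.

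| Baseline (×ULN) | Retest only above | Uncovered band | Width |
|---|---|---|---|
| 2.6 | 5.2 | 5.0–5.2 | 0.2 |
| 2.8 | 5.6 | 5.0–5.6 | 0.6 |
| 3.0 | 6.0 | 5.0–6.0 | 1.0 |
| 3.5 | 7.0 | 5.0–7.0 | 2.0 |

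For example, 5.5×ULN from Baseline 2.8 is 5.5/2.8 = 1.96-fold: above the stop level, below the trigger. The 3.5 row is possible because the entry limit applies at Screening to unexplained, confirmed elevations, while Baseline is the last pre-dose value. From Baseline 4.0 upward, 2 × Baseline reaches 8×ULN, where the immediate stop takes over.

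**Step 3: when the next scheduled value arrives.** The range adds or subtracts the windows of both visits (3 + 7 = 10 days, or 7 + 7 = 14 days).

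| Value first seen at | Days to next test (range) | Less 14 days (range) |
|---|---|---|
| Day 30 | 84 − 30 = 54 (44–64) | 40 (30–50) |
| Day 84 | 180 − 84 = 96 (82–110) | 82 (68–96) |
| Day 180 | 270 − 180 = 90 (76–104) | 76 (62–90) |
| Day 270 | 365 − 270 = 95 (81–109) | 81 (67–95) |

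The gaps are 44/14 = 3.1 to 110/14 = 7.9 times the 14-day criterion. The last column is the worst-case time beyond 14 days before a scheduled sample could show persistence, assuming no unscheduled test.

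**Step 4: the other reading.** If a more than 2-fold change meant an increase of more than 200%, the trigger would be above 3 × Baseline. It would then pass 5×ULN at Baseline 5/3 = 1.67×ULN, and the gap would be wider.

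**The case against.** The strongest reply is that the stop rule itself implies the repeat. It applies at any Baseline, and ALT and AST results are not blinded (Section 7.1 blinds lipid values only). An Investigator who sees 5.5×ULN cannot apply a 2-week rule without another value. Section 8.1 requires clinically significant laboratory values to be followed with repeat tests, Section 4.3 allows drug to be stopped for a severe laboratory abnormality, and Section 5.4 asks Investigators to treat everyone as if on obicetrapib. The Laboratory Manual, which is not among the documents, may flag ALT or AST in this range. This makes a missed repeat less likely, and it stands to that extent. But none of these provisions sets an ALT/AST retest level or interval that can be seen. Event-of-special-interest review orders no retest either.

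The affected group is also small. Known liver disease and CK above 3×ULN are excluded. The participant must have no symptoms, no bilirubin or INR criterion met and the other enzyme below its own trigger, and the elevation must persist. This stands; the documents give no count.

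A Baseline-relative trigger is also a reasonable way to avoid repeated alarms from chronic elevation. That justifies the relative trigger, but not letting it rise above the level at which a stopping rule applies.

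A reader might infer that the guideline never asks for a retest when Baseline exceeds 2.5×ULN. It does: any value above twice Baseline prompts one. Nor may the overruns in Step 3 be read as expected delays; they assume that nobody acts on a visible result.

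**Conclusion.** The gap is real but narrow. Within Section 8.1.4.1, for a symptom-free participant with Baseline ALT or AST above 2.5×ULN, a value above 5×ULN but not above twice Baseline prompts no 48 to 72 hour retest, although the duration stop depends on a second value. The band is 0.6×ULN wide at Baseline 2.8 and 1.0×ULN at 3.0. A reader might take 1.0×ULN as its maximum; the documents do not support that, because a Day 1 value above 3×ULN would widen it.

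Not affected are values above twice Baseline, the 8×ULN stop, the bilirubin, INR and symptom criteria, and cases where the other enzyme meets its own trigger. The efficacy analysis is not affected.

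The conclusion rests on reading the trigger as twice Baseline and on the documents supplied; a critical-value flag in the Laboratory Manual could narrow the gap in practice. Probably very few participants are concerned. The point should still be corrected, because two stated safety rules do not fit together and the remedy is cheap.

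**What to change.** In Section 8.1.4.1, extend the symptom-free retest trigger so that it reads: more than 2-fold change (if abnormal at Baseline), or above 5×ULN regardless of Baseline. The retest level then cannot exceed the duration-stop level, and the existing confirmation and serial testing follow.

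This is a one-line clarification or amendment. It costs a few unscheduled blood draws, plus the section's follow-up when a value is confirmed. Small fluctuations would rarely set it off: passing 5×ULN takes a rise of more than 5/2.6 = 1.92-fold from Baseline 2.6, 5/2.8 = 1.79-fold from 2.8 and 5/3.0 = 1.67-fold from 3.0. A Day 1 Baseline of 3.5 would need less (5/3.5 = 1.43-fold).
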